6.3.4 Replacement of withdrawn patients

Withdrawn patients will not be replaced.

6.4 Study treatment(s) and concomitant therapy

Study treatments/interventions are all pre-specified interventions (e.g., clinical assessments and behavioral) intended to be administered to the study participants during the study conduct.

Sobi

Eftrenonacog alfa/Alprolix® - Efmoroctocog alfa/Elocta®

Clinical Study No: Sobi.HAEM89-007

Both rFVIIIFc and rFIXFc will be used as per clinical routine for each patient and their use will not be dictated by the protocol.

6.4.1 Prior and concomitant therapy

Therapies considered necessary for the patient's welfare may be given at the discretion of the investigator. Pain, anti-inflammatory and anti-depressant therapies used in the month preceding baseline/every follow-up visit must be recorded in the CRF. No medicinal product under investigation may be used in this study.

6.4.2 Treatment compliance

Treatment compliance, as assessed by the investigator, will be recorded in the CRF.

Sobi

Eftrenonacog alfa/Alprolix® - Efmorococog alfa/Elocta®

Clinical Study No: Sobi.HAEM89-007

6.5 Effectiveness and safety assessments

6.5.1 Study schedule

6.5.1.1 Schedule of events

Tests and Assessments	Enrolment Visit (Visit 0) ¹	Baseline Visit (Visit 1) ¹	Follow-up Visits		
			Month 6 (Visit 2) (± 28 days)	Month 12 (Visit 3) (± 28 days)	Month 18, End of Study (Visit 4) (- 28 days and + 56 days)
Informed Consent and Assent	X	X			
Review of eligibility criteria	X	X			
Sex	X	X			
Age	X	X			
Height	X	X	X ²	X ²	X ²
Weight	X	X	X	X	X
Haemophilia history	X	X			
Medical and surgical history	X	X			
Information on surgery, including joint surgery, and interventions	X	X	X	X	X

Sobi

Eftrenonacog alfa/Alprolix® - Efmorococog alfa/Elocta®

Clinical Study No: Sobi.HAEM89-007

Tests and Assessments	Enrolment Visit (Visit 0) ¹	Baseline Visit (Visit 1) ¹	Follow-up Visits		
			Month 6 (Visit 2) (± 28 days)	Month 12 (Visit 3) (± 28 days)	Month 18, End of Study (Visit 4) (- 28 days and + 56 days)
Pain, anti-inflammatory and anti-depressant therapies used in the month preceding baseline/ at every follow-up visit	X	X	X	X	X
Bleeding information ³	X ⁴	X ⁴	X	X	X
Prescribed rFVIIIFc or rFIXFc dose and injection frequency	X ⁴	X ⁴	X	X	X
Reason for change of haemophilia treatment (if applicable)	X	X	X	X	X
Factor rFVIIIFc or rFIXFc plasma activity levels, if available	X ⁴	X ⁴			X
Ultrasound (HEAD-US) score	X	X	X	X	X
Hemophilia Joint Health Score (HJHS)	X	X			X
Target joints presence and location	X	X			
Impaired joints presence and location	X	X			
PROs	X	X			X

Sobi

Eftrenonacog alfa/Alprolix® - Efmoroctocog alfa/Elocta®

Clinical Study No: Sobi.HAEM89-007

Tests and Assessments	Enrolment Visit (Visit 0) ¹	Baseline Visit (Visit 1) ¹	Follow-up Visits		
			Month 6 (Visit 2) (± 28 days)	Month 12 (Visit 3) (± 28 days)	Month 18, End of Study (Visit 4) (- 28 days and + 56 days)
Physician judgement of patient's treatment adherence to rFVIIIFc or rFIXFc	X ⁴	X ⁴	X	X	X
Data from florio HAEMO (estimated FVIII and FIX levels, physical activity levels, duration and type, bleeding episodes, pain, well-being, rFVIIIFc/rFIXFc dosing and adherence) ⁵	X	X	X	X	X
Questionnaire on impact of florio HAEMO on patients' sense of protection and their activity level	X ⁶	X ⁶			
Safety assessments ⁷		X	X	X	X
SAEs ⁸	X	X	X	X	X

Abbreviations: HEAD-US: haemophilia early arthropathy detection with ultrasound; HJHS: hemophilia joint health score; PRO: patient-reported outcome; SAE: serious adverse event

1. The enrolment and baseline visit may be performed either on the same day or divided over more than one day. Assessments should only occur once, i.e. no repeat measurements are needed for an assessment performed at enrolment. A time window of +28 days from the enrolment visit is allowed, if it is not possible to perform all assessments at the same time.
2. For patients younger than 18 years of age, height is recorded at all routine clinical visits. For adult patients, height is only recorded at the enrolment visit.
3. With the following captured for each bleeding episode, if available: bleeding episode circumstance (e.g. spontaneous, traumatic, surgery), bleeding location (e.g. muscle, elbow, knee, ankle, other), date of bleeding, number of injections to treat the bleeding episode, and dose (IU) used to treat the bleeding episode.
4. Including the 6-month period prior to enrolment
5. For patients who have used florio HAEMO for at least 3 months and consented to the use of data from florio HAEMO. Data will be retrospectively collected from the 6-month period prior to enrolment in the sub-study/main study, and until end of study.

Sobi

Eftrenonacog alfa/Alprolix® - Efmoroctocog alfa/Elocta®

Clinical Study No: Sobi.HAEM89-007

- 6. Patients participating in the florio HAEMO sub-study will be asked to complete a questionnaire once. It can occur at baseline or any time during the main study, if they enrol in the sub-study after the baseline visit.
- 7. Refer to section “safety assessments” for the safety events to be captured.
- 8. All SAEs (including medically important AEs) from the Enrolment visit to the patient’s last study visit.

Sobi

Eftrenonacog alfa/Alprolix® - Efmorocog alfa/Elocta®

Clinical Study No: Sobi.HAEM89-007

6.5.1.2 Visit 0/1 – Enrolment/Baseline

In this study, assessments related to enrolment and baseline may be performed either on the same day or divided over more than one day, depending on the availability of the patient and the site personnel. A time window of +28 days from the enrolment visit is allowed, if it is not possible to perform all assessments at the same time. No assessments may be performed prior to obtaining signed informed consent. The date when the HEAD-US assessment is performed will be considered as the baseline visit date and will be used to calculate the timepoints for the follow-up visits.

At the enrolment visit and prior to any study-related activities the patient/the patient's legally authorized representative have to sign and date the informed consent form.

The inclusion and exclusion criteria will be reviewed and recorded (see sections 6.3.1 and 6.3.2).

Data will be collected in accordance with the schedule of events (see section 6.5.1.1).

6.5.1.3 Visit 2 – Month 6

Data will be collected in accordance with the schedule of events (see section 6.5.1.1).

All study assessments should be performed within a ±28 days time window.

6.5.1.4 Visit 3 – Month 12

Data will be collected in accordance with the schedule of events (see section 6.5.1.1).

All study assessments should be performed within a ±28 days time window.

6.5.1.5 Visit 4 – Month 18/End of study

Data will be collected in accordance with the schedule of events (see section 6.5.1.1).

All study assessments should be performed within a -28 and +56 days time window. The date of the last assessment should be considered as the EOS date.

If a patient prematurely withdraws from the study and more than 3 months since the last study visit have passed, all assessments should be performed to the extent possible. If a patient withdraws from the study less than 3 months since the last visit, PRO collection and HJHS assessment should be performed to the extent possible.

6.5.2 Demography

Demographics includes age at screening (year of birth), sex, weight and height. The body weight recordings will be repeated at each visit. Height will be measured at the baseline visit for all patients, thereafter only for patients <18 years old. Body mass index will be calculated based on the weight and height measurements.

6.5.3 Haemophilia history

Haemophilia history will be collected at the baseline/enrolment visit including the following:

- severity of disease
- type of haemophilia
- age at diagnosis
- inhibitor history
- type of prophylactic treatment (primary, secondary or tertiary prophylaxis)
- age at prophylaxis initiation
- haemophilia prescription information (product, regimen, and dosing) from the 6 months period prior to enrolment
- haemophilia prescription information (product, regimen, and dosing) at time of enrolment
- previous non-factor therapy (product, start and stop date)
- bleeding episodes (location, spontaneous/traumatic) from the 6 months prior to enrolment
- date of first injection with rFVIIIFc or rFIXFc

6.5.4 Medical and surgical history

Significant medical and surgical history during at least the previous 6 months before enrolment will be collected.

Medical history includes any significant medical condition, including the following:

- history of allergy/anaphylactic shock
- HIV
- hepatitis B and C infection status
- clinically significant liver, renal, cardiovascular diseases
- clinical depression
- non-haemophilic acute or chronic medical conditions causing mobility/joint problems
- other coagulation disorder(s) in addition to haemophilia A or B

For surgical history, orthopaedic or musculoskeletal surgical or other interventions are of special interest. Information on date and type of intervention will be collected; for surgical interventions also classification in major/minor.

Data on surgical and other interventions related to joints will be collected for all joints and for anytime in the past.

6.5.5 Surgical and other interventions

Information on joint related surgeries and other interventions (including, but not limited to orthopaedic interventions, synoviorthesis (radio- and chemical)) will be collected. Moreover, any additional joint assessments including MRI, X-ray, and ROM will be documented. Information

Sobi

Eftrenonacog alfa/Alprolix® - Efmorocog alfa/Elocta®

Clinical Study No: Sobi.HAEM89-007

on non-joint related surgeries, including tooth extractions, (type, date, classification (major/minor), related bleeding episodes) will be separately collected.

6.5.6 Target and impaired joints

At baseline, information on target joints (presence and location) will be recorded as per the assessment of the investigator. For the follow-up visits, resolution/reccurence/development of target joints will be calculated based on the investigator reported bleeds, as per the target joint definitions for resolution, recurrence and development (1).

Information on the presence, location and related assessments of impaired joints will be recorded as per the assessment of the investigator. A joint can simultaneously be a target joint and an impaired joint. The status of an impaired joint will be assessed at the baseline visit, and details on clinical/functional investigations performed as well as any changes in e.g. pain will be collected.

6.5.7 Concomitant therapy

Pain, anti-inflammatory and anti-depressant therapies used in the month preceeding baseline/ every follow-up visit will be collected.

6.5.8 Bleeding episodes

For any bleeding episode, the following will be collected:

- bleeding episode circumstance (e.g. spontaneous, traumatic)
- bleeding episode location (e.g. muscle, joint, other)
- date of bleeding episode
- dose (IU) and number of injections used to treat the bleed

6.5.9 Haemophilia treatment

The prescribed rFVIIIFc or rFIXFc dose (IU) and injection frequency will be collected at each follow-up visit.

Any change in haemophilia treatment (dose, injection frequency or any other change in management, for example physiotherapy) will be collected at each visit.

FVIII or FIX plasma activity levels, including dose administered (IU) and time since last dose (h) will be collected if available.

Physician judgement of patient's treatment adherence to rFVIIIFc or rFIXFc will be collected at each visit.

Sobi

Eftrenonacog alfa/Alprolix® - Efmorocog alfa/Elocta®

Clinical Study No: Sobi.HAEM89-007

6.5.10.2 Functional joint examination – HJHS

At the baseline and month 18 (EOS) visits, the investigator or delegate will assess joint structure/function using the HJHS scoring system version 2.1 (27, 28). The person who performs the assessment should be properly trained and for consistency it is recommended that the same person performs the assessment at each study visit. The six index joints (elbows, knees and ankles) will be examined and scored. The score for each joint is the sum of the individual item scores for the 8 dimensions. Global gait is assessed separately.

Sobi

Eftrenonacog alfa/Alprolix® - Efmorocog alfa/Elocta®

Clinical Study No: Sobi.HAEM89-007

Swelling	Crepitus on Motion	Strength (Using The Daniels & Worthingham's scale)
0 = No swelling	0 = None	Within available ROM
1 = Mild	1 = Mild	0 = Holds test position against gravity with maximum resistance (gr.5)
2 = Moderate	2 = Severe	1 = Holds test position against gravity with moderate resistance (but breaks with maximal resistance) (gr.4)
3 = Severe		2 = Holds test position with minimal resistance (gr. 3+), or holds test position against gravity (gr.3)
Duration	Flexion Loss	3 = Able to partially complete ROM against gravity (gr.3-2+), or able to move through ROM gravity eliminated (gr.2), or through partial ROM gravity eliminated (gr.2-)
0 = No swelling or < 6 months	0 = < 5°	4 = Trace (gr.1) or no muscle contraction (gr.0)
1 = > 6 months	1 = 5° - 10°	NE = Non-Evaluable
	2 = 11° - 20°	
	3 = > 20°	
Muscle Atrophy	Extension loss (from hyperextension)	Global Gait (walking, stairs, running, hopping on 1 leg)
0 = None	0 = < 5°	0 = All skills are within normal limits
1 = Mild	1 = 5° - 10°	1 = One skill is not within normal limits
2 = Severe	2 = 11° - 20°	2 = Two skills are not within normal limits
	3 = > 20°	3 = Three skills are not within normal limits
Joint Pain		4 = No skills are within normal limits
0 = No pain through active range of motion		NE = Non-Evaluable
1 = No pain through active range; only pain on gentle overpressure or palpation		
2 = Pain through active range		

The minimum score per joint is 0, the maximum score is 20.

The total joint score (range 0-120) is the sum of the 6 joint scores. The HJHS total score is total joint score + global gait (range 0-4); minimum score 0, maximum 124.

6.5.10.3 Patient-Reported Outcomes

Patient questionnaires will be administered at the baseline and 18 months (EOS), to evaluate and compare changes in patients' perceptions of pain and physical activity/function. PRO questionnaires will be completed by patients or caregivers depending on age, see Table 1 for additional details. When possible, caregivers of paediatric patients less than 8 years old will complete the PRO instruments verbatim based on the patient's responses. Patients and/or caregivers will be encouraged to complete the PROs based on the patient's age at enrolment. It is expected that it will take approximately 8-10 minutes per visit to complete all questionnaires. The PROs are expected to be completed on paper and the paper forms will be considered as the source document for the PRO data. Due to language availability, not all patients may be required to complete all PROs.

Sobi

Eftrenonacog alfa/Alprolix® - Efmoroctocog alfa/Elocta®

Clinical Study No: Sobi.HAEM89-007

Table 1 PRO questionnaires

Instrument	Patients aged ≥6 - <12 years	Patients aged >8 - 17 years	Patients aged ≥18 years
PROMIS Pain intensity 3a			X
PROMIS Paediatric pain intensity 1a		X ²	
PROMIS Parent proxy pain intensity 1a	X ¹		
PROMIS Pain interference short form 6a			X
PROMIS Paediatric pain interference short form 8a		X ²	
PROMIS Parent proxy pain interference	X ¹		
PROMIS Physical function/activity short form 6b			X
PROMIS paediatric physical activity short form 8a		X ²	
PROMIS parent proxy physical activity short form 8a	X ¹		
IPAQ-SF			X ³

Abbreviations: IPAQ-SF: International Physical Activity Questionnaire - Short Form; PRO: patient-reported outcome; PROMIS: Patient-Reported Outcomes Measurement Information System

¹ PRO completed on behalf of the patient by the caregiver as proxy

² PRO completed on behalf of the patient by the caregiver, or by the patient, if possible

³ Age range to be aligned with questionnaire age range

Information on whether questionnaires are completed by the patient or by a caregiver will be collected and accounted for in the statistical analysis.

6.5.10.3.1 PROMIS

PROMIS is a validated system of reliable and precise measures of patient-reported health status (29). The PROMIS initiative is part of the National Institute of Health (NIH) goal to develop systems to support NIH-funded research across all its institutes and centers. PROMIS measures cover physical, mental and social health and can be used for many chronic conditions. These questionnaires use a 5-point Likert response scale and a recall period of the past 7 days.

6.5.10.3.1.1 PROMIS Pain intensity (Pain intensity 3a (adults), paediatric pain intensity 1a, parent proxy pain intensity 1a)

Measures how much a person hurts. There are 3 questions for adults and 1/1 questions for children/parents. It takes less than a minute to complete.

Sobi

Eftrenonacog alfa/Alprolix® - Efmorocog alfa/Elocta®

Clinical Study No: Sobi.HAEM89-007

6.5.10.3.1.2 **PROMIS Pain interference** (pain interference - short form 6a, paediatric pain interference short form 8a, parent proxy pain interference)

Measures consequences of pain on relevant aspects of one's life. This includes the extent to which pain hinders engagement with social, cognitive, emotional, physical, and recreational activities. There are 6 questions for adults and 8/13 questions for children/parents. It takes 1-2 minutes to complete.

6.5.10.3.1.3 **PROMIS Physical function / activity** (physical function - short form 6b, paediatric physical activity -short form 8a, parent proxy physical activity short form 8a)

Includes the functioning of one's upper extremities (dexterity), lower extremities (walking or mobility), and central regions (neck, back), as well as instrumental activities of daily living. There are 6 questions for adults and 8/8 questions for children/parents. It takes 1-2 minutes to complete.

6.5.10.3.2 **IPAQ-SF**

The IPAQ-SF is a validated, 7-day recall questionnaire suitable for people between 15-69 years of age to measure current levels of physical activity (30). IPAQ-SF assesses physical activity across domains; leisure-time physical activity, domestic and gardening activities, work-related physical activity and transport-related physical activity. The items are structured to provide separate domain specific scores for walking, moderate-intensity and vigorous-intensity activity within each of the work, transportation, domestic chores and gardening (yard) and leisure-time domains. Scoring of the IPAQ-SF results in a continuous variable in the form of total MET-minutes per week, as well as categorization into high, moderate or low physical activity level. The IPAQ-SF will be administered at baseline and at the yearly visits. It is expected to take approximately 5 minutes to complete.

6.5.11 **Exploratory endpoints - florio HAEMO sub-study**

If a patient has used florio HAEMO (a certified medical device used in routine clinical practice) for at least 3 months and agrees to have data collected from it by providing informed consent, the patient can participate in the florio HAEMO exploratory sub-study.

A questionnaire on the impact of florio HAEMO on patients' sense of protection and their physical activity level will be administered, and data from florio HAEMO on estimated FVIII levels, physical activity levels, bleeds, pain, well-being and rFVIIIFc/rFIXFc dosing will be collected. Data will be retrospectively collected from the 6-month period prior to enrolment, and until EOS.

6.5.11.1 **florio HAEMO patient questionnaire**

All patients who use florio HAEMO to monitor their haemophilia, or their caregivers for patients <12 years of age (Table 2), and who consent to the use of florio HAEMO data in the study, will

Sobi

Eftrenonacog alfa/Alprolix® - Efmorocog alfa/Elocta®

Clinical Study No: Sobi.HAEM89-007

be asked to complete a questionnaire (Appendix 2 and Appendix 3) including questions about their use of florio HAEMO, and if florio HAEMO has an impact on their sense of protection and activity level. The questionnaire will be completed one time during the study and administered once a patient has used florio HAEMO for at least 3 months.

Table 2 florio HAEMO patient questionnaire

Instrument	Patients aged <8 years	Patients aged 8 to <12 years	Patients aged 12 to <18 years	Patients aged ≥18 years
florio HAEMO Patient Questionnaire	x ^{1, 2}	x ^{1, 2}	x ²	x ²

¹ Questionnaire completed on behalf of the patient by the caregiver as proxy

² Questionnaire only completed by patients that are using florio HAEMO to monitor their haemophilia

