STUDY OBJECTIVES	
Primary objective:	To evaluate the overall joint status as detected by ultrasound (US) in haemophilia A and B patients treated with efmoroctocog alfa (rFVIIIfc) or eftrenonacog alfa (rFIXFc) prophylaxis over the 18-month study period.
Secondary objectives:	
 • To evaluate the joint status as detected by US in the Haemophilia Early Arthropathy Detection with Ultrasound (HEAD-US) specific items of hypertrophic synovium, cartilage and bone damage in haemophilia A and B patients treated with rFVIIIfc or rFIXFc prophylaxis over the 18-month study period • To evaluate the clinical joint status as detected by Hemophilia Joint Health Score (HJHS) in haemophilia A and B patients treated with rFVIIIfc or rFIXFc prophylaxis over the 18-month study period • To evaluate the presence, resolution, recurrence and new development of target joints in haemophilia A and B patients treated with rFVIIIfc or rFIXFc prophylaxis over 18 months • To describe the bleeding episodes in haemophilia A and B patients treated with rFVIIIfc or rFIXFc prophylaxis over the 18-month study period • To evaluate the quality of life in haemophilia A and B patients treated with rFVIIIfc or rFIXFc prophylaxis over the 18-month study period
Exploratory objectives – florio® HAEMO sub-study:	
 • Impact of florio HAEMO on patients' sense of protection and their physical activity level in haemophilia A and B patients treated with rFVIIIfc or rFIXFc prophylaxis • Explore adherence to prescribed treatment regimen in haemophilia A and B patients treated with rFVIIIfc or rFIXFc prophylaxis • Explore relationship between estimated FVIII and FIX levels and physical activity in haemophilia A and B patients treated with rFVIIIfc or rFIXFc prophylaxis • Explore timing of bleeding episodes in relation to estimated FVIII and FIX levels and physical activity in haemophilia A and B patients treated with rFVIIIfc or rFIXFc prophylaxis • Explore the use of florio HAEMO to characterise pain and well-being in haemophilia A and B patients treated with rFVIIIfc or rFIXFc prophylaxis
STUDY ENDPOINTS	
Primary endpoint:	
 • Change from baseline in total HEAD-US score up to month 18 (end of study - EOS).

Confidential

Page 6 of 56

Version 1.0 Final 15 November 2022

Sobi

Eftrenonacog alfa/Alprolix® - Efmorococog alfa/Elocta®

Clinical Study No: Sobi.HAEM89-007

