Secondary endpoints:	
 Change from baseline in HEAD-US score for hypertrophic synovium at 6, 12 and 18 months Change from baseline in HEAD-US score for cartilage at 6, 12 and 18 months Change from baseline in HEAD-US score for bone at 6, 12 and 18 months Change from baseline in total HJHS at month 18 (EOS) Number and location of target joints at baseline, 6, 12 and 18 months Total Annualized bleeding rate (ABR), joint ABR, target joint ABR, traumatic/spontaneous ABR Patient-Reported Outcomes Measurement Information System (PROMIS) physical function/activity scores at baseline and 18 months PROMIS pain intensity and interference scores at baseline and 18 months IPAQ-SF scores at baseline and 18 months
Exploratory endpoints – florio HAEMO sub-study:	
 Results from questionnaire on impact of florio HAEMO tools on patients' sense of protection and their physical activity level florio HAEMO captured treatment adherence scores florio HAEMO captured estimated FVIII and FIX levels florio HAEMO captured physical activity type, duration and intensity florio HAEMO captured bleed data (timing, location, cause, treated/untreated) florio HAEMO captured FVIII/FIX administration data (time, dose) florio HAEMO captured pain data (time, location, cause, intensity) florio HAEMO captured well-being data
STUDY DESIGN AND METHODS	

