Assessments:	
 • At each visit HEAD-US assessments will be performed. Information on pain, anti-inflammatory and anti-depressant medications will be recorded • At enrolment/baseline and EOS, PROs will be completed • At enrolment/baseline and EOS, HJHS will be assessed • For patients participating in the florio HAEMO sub-study a questionnaire on the impact of florio HAEMO on patients' sense of protection and their physical activity level will be administered when they enter the sub-study. Data from the florio HAEMO app will be collected 
Safety Assessments:
 
The following safety events should be collected:
 
 • Serious Adverse Events (SAEs) • Non-serious Adverse Events (AEs) assessed as causally related to treatment with rFVIIIFc or rFIXFc and considered unexpected • AEs of special interest: inhibitor development, thrombotic events and serious hypersensitivity reaction including anaphylactic reactions • AEs leading to premature discontinuation of rFVIIIFc or rFIXFc • Exposure during pregnancy, medication errors, misuse or abuse in relation to rFVIIIFc or rFIXFc 
Any AE suspected to be causally related to a medicinal product other than the studied Sobi product, and which does not result from a possible interaction with it, should be reported by the Investigator to the concerned authority via the national reporting system, or to the Marketing Authorization Holder of the suspected medicinal product.

Confidential

Page 8 of 56

Version 1.0 Final 15 November 2022

Sobi

Eftrenonacog alfa/Alprolix® - Efmoroctocog alfa/Elocta®

Clinical Study No: Sobi.HAEM89-007

Test product; dose and mode of administration:	N/A																							
Reference product; dose and mode of administration:	N/A																							
Auxiliary medicinal products:	N/A																							
Duration of treatment(s):	According to routine clinical practice																							

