31 International Committee of Medical Journal Editors. Recommendations for the conduct, reporting, editing, and publication of scholarly work in medical journals: updated December 2016 [Internet]. International Committee of Medical Journal Editors (ICMJE); 2016. [cited 2017 Jan 12]. Available from: <http://www.icmje.org/recommendations/>

Sobi

Eftrenonacog alfa/Alprolix® - Efmorocog alfa/Elocta®

Clinical Study No: Sobi.HAEM89-007

Appendix 1

Study Administrative Structure

Monitoring: IQVIA Ltd., Reading, United Kingdom

SAE reporting: Shared responsibility between IQVIA Ltd., Reading, United Kingdom and Swedish Orphan Biovitrum AB (publ), Stockholm, Sweden

Data management: IQVIA Ltd., Reading, United Kingdom

Statistics: IQVIA Ltd., Reading, United Kingdom

Sobi

Eftrenonacog alfa/Alprolix® - Efmorocog alfa/Elocta®Clinical Study No: Sobi.HAEM89-007**Appendix 2****florio HAEMO Patient Questionnaire****florio HAEMO Effect on Sense of Protection & Activity Level**

Have you used any other haemophilia management tool before?

- Yes
- No

If yes; enter the one(s) you have you used: _____

How often did you use florio HAEMO to monitor your estimated FVIII or FIX levels in the last month?

- Daily
- A few times per week
- Once weekly
- A few times per month
- Never

Since you started using florio HAEMO, do you feel more in control of your haemophilia?

- In much better control
- In better control
- No difference
- In worse control
- In much worse control

Since you started using florio HAEMO, do you feel more protected against bleeds?

- Much more protected
- More protected
- No difference
- Less protected
- Much less protected

Has florio HAEMO helped you in choosing the timing of your physical activities?

- Yes
- No

Has florio HAEMO helped you to facilitate care planning and potential treatment adjustment discussions with your health care provider?

- Yes
- No

Would you recommend the use of florio HAEMO to other haemophilia patients?

- Yes
- No

Confidential

Page 53 of 56

Sobi

Eftrenonacog alfa/Alprolix® - Efmoroctocog alfa/Elocta®

Clinical Study No: Sobi.HAEM89-007

If you answered no, can you comment on the reason(s)?

Patient Study ID: _____

Date of completion: _____

Version 1.0 Final 15 November 2022

Confidential

Page 54 of 56

Version 1.0 Final 15 November 2022

Sobi

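### The florio HAEMO patient form asks about the timing of physical activity but not about change in activity level, so it cannot deliver that part of its exploratory endpoint; separately, one IPAQ-SF timing sentence needs reconciling

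*Combined protocol and SAP*

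**What the plan says.** The exploratory objective, in the synopsis and in section 5.3, is "Impact of florio HAEMO on patients' sense of protection and their physical activity level". The matching endpoint, in the synopsis and in section 5.3.1, is "Results from questionnaire on impact of florio HAEMO tools on patients' sense of protection and their physical activity level". Section 6.5.11.1 says that participants will complete a form "including questions about their use of florio HAEMO, and if florio HAEMO has an impact on their sense of protection and activity level". The form in Appendix 2 is headed "florio HAEMO Effect on Sense of Protection & Activity Level". Section 6.5.11.1 and note 6 to the schedule of events say that it is completed once.

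The one activity item on the form is "Has florio HAEMO helped you in choosing the timing of your physical activities", answered yes or no. Sense of protection has a five-point change item: "Since you started using florio HAEMO, do you feel more protected against bleeds". Sense of control has one in the same format.

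On a separate matter, section 6.5.10.3.2 places IPAQ-SF at baseline and at yearly visits. The secondary endpoints (synopsis and 5.2.1) and the analysis in 8.3.4 use baseline and 18 months.

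**The concern.** Activity level is named beside sense of protection almost everywhere the questionnaire is described, yet only protection has an item that measures change. A yes to the timing item gives neither the direction nor the size of any change in level. A patient who moved the same activity to another day and a patient who became much more active could both answer yes. Because the form is completed once, what it omits is not collected later. The endpoint would then be reported with one of its two named components missing, or with the timing item standing in for level under a title that promises level.

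For IPAQ-SF, a site that follows 6.5.10.3.2 literally would collect an unscheduled form at month 12 and might omit the month-18 form on which the endpoint and analysis depend.

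**Working it through.** The protocol states no figure on this point, so the check is a count and a side-by-side reading.

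**Where activity level is promised.**
- As the objective: synopsis and 5.3, which is 2 places.
- As the questionnaire's purpose or endpoint: synopsis endpoints, synopsis assessments, 5.3.1, the schedule-of-events row in 6.5.1.1, 6.5.11, 6.5.11.1, 8.3.5 and the heading of Appendix 2, which is 8 places.
- Total: 2 + 8 = 10. Nine of these say impact and one (the form's heading) says effect.
- Section 4.2 also describes a questionnaire on activity levels during use of the app, but makes no claim about impact. It is not counted.

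**What the patient form asks (Appendix 2).**

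| Closed item | Subject | Response |
|---|---|---|
| 1 | Other management tools used before | yes/no, with free text naming them |
| 2 | How often factor-level estimates were checked | five options |
| 3 | Sense of control | five-point change |
| 4 | Sense of protection | five-point change |
| 5 | Help in choosing when to be active | yes/no |
| 6 | Help with care-planning discussions | yes/no |
| 7 | Would recommend the app | yes/no, with free-text reason if no |

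Closed items: 4 yes/no + 3 five-option = 7. With the 2 free-text follow-ups there are 7 + 2 = 9 fields. On protection: 1 of 7. On timing of activity: 1 of 7. On change in activity level: 0 of 7 closed items and 0 of 9 fields.

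**Whether other data supply the missing answer.**
- App-captured activity type, duration and intensity is a separate endpoint in 5.3.1. It describes activity and does not record what patients attribute to the app.
- Entry to the sub-study requires at least 3 months of app use (6.3.1.1). The app data reach back 6 months before enrolment (note 5 to the schedule), but the plan guarantees no period before app use to compare with.
- PROMIS and, for eligible ages, IPAQ-SF measure function or activity at baseline and month 18 without reference to the app.

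**IPAQ-SF timing.** Visits are at baseline and months 6, 12 and 18 (6.1, 6.5.1.1). The only post-baseline visit that falls on a whole year is month 12. The schedule has PROs at enrolment/baseline and month 18 and none at month 12. Three places name IPAQ-SF at baseline and 18 months (synopsis endpoints, 5.2.1, 8.3.4). Three more cover it as a PRO at baseline and month 18 or end of study (synopsis assessments, the schedule, 6.5.10.3). The single sentence in 6.5.10.3.2 stands against all six.

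**The case against.** The best defence is that timing is itself an effect on activity. Section 4.1 says that patients may hold back from activity when they do not know their factor level, so choosing when to be active in light of an estimated level is a plausible way for the app to act. This stands as far as it goes: the timing item is relevant, attributes its effect to the app, and can be reported. It is still not level, and level is what the objective, the endpoint and the form's own heading name.

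A second defence is that activity is well covered elsewhere, and that the objective in the synopsis and 5.3 does not name the questionnaire as its only source. That also stands. A reader might infer that the sub-study cannot describe activity at all, or that the whole objective fails. The documents do not support this, because app data, PROMIS and IPAQ-SF all bear on activity or function. What is missing is the patient-reported impact that the questionnaire endpoint names.

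A reader might also infer that the gap covers every age group. The contents page lists a caregiver form as Appendix 3, but its text was not available, so nothing can be said about it. That the patient form is self-completed only from age 12 is itself an inference from 6.5.11.1 and Table 2. Table 2 marks the patient questionnaire in all four age columns, with proxy completion below 12.

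Finally, the repetition adds little weight. The synopsis objective and endpoint duplicate 5.3 and 5.3.1, and the finding would be the same with fewer mentions.

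**Conclusion.** The point holds and is minor. The Appendix 2 form, as drafted, supports statements about sense of protection and about timing of activities, but not about change in activity level. The reach is one component of one exploratory endpoint in an optional sub-study, with no hypothesis testing planned and no sub-study size given. The conclusion assumes that Appendix 2 is complete as shown; it runs through to the patient ID and completion-date lines.

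The IPAQ-SF sentence is a separate inconsistency that touches a secondary endpoint. A reader might infer that month-18 IPAQ-SF values will be lost. The documents do not show that: where sites follow the schedule of events, the month-18 form is collected.

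**What to change.** **Patient form.** Add one item to Appendix 2 after the protection item, in the existing five-point format, with a stem that matches its responses. For example: *Since you started using florio HAEMO, how has your physical activity level changed?* (much more active / more active / no difference / less active / much less active). Check Appendix 3 for a matching item. Have the SAP describe the result as uncontrolled, self-reported change since starting the app, not change caused by it. Report how many patients completed the form before the item was added.

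If no item is added to Appendix 2, restate the questionnaire endpoint (2 places) and the questionnaire descriptions (6 places, including the form's heading) for patient-completed forms as sense of protection and timing of physical activities, and align the sentence in 4.2. Do this whatever Appendix 3 contains. The broader objective in the synopsis and 5.3 may stay if the app activity data are named as its descriptive source.

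**Cost.** A small amendment with ethics approval (3.1), translation of one item for approximately 11 countries (6.1; the number of languages is not given), and missing answers from patients who have already completed the form. No visit is added. Restating adds no item, but it changes the text in those places and the patient-facing heading, which would need retranslation.

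**IPAQ-SF.** In 6.5.10.3.2, replace the reference to yearly visits so that the timing reads baseline and month 18 (EOS). This is a one-phrase correction.
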